# 6.2 Dose Interruptions/Withholding

Study treatment may be withheld from a subject based on the investigator's decision in the event of intercurrent illness, AE, administrative reasons, or other reasons. If the subject's condition subsequently improves, or the situation that resulted in withholding study drug rectifies itself, the investigator may resume dosing as soon as possible, unless the delay is more than 4 weeks.

Dosing should be delayed for any DLT-equivalent toxicity and possible National Cancer Institute Common Terminology Criteria for Adverse Events (NCI-CTCAE) > Grade 2 AEs considered related to study medication. At the investigator's discretion, dosing may recommence when the toxicity has resolved to Grade 2 or less. Immune-related reactions or allergy should resolve to  $\leq$  Grade 1.

Treatment will be discontinued if a treatment-emergent AE (TEAE) has not resolved (to acceptable grade) after  $\leq$  3 weeks.

# 6.3 Supportive Management

# 6.3.1 Cardiac Monitoring

This section outlines the requirements for proceeding with treatment with APR-246, and the protocol rules for APR-246 dose modification due to AEs.

At screening, 12-lead ECGs should be collected in triplicate to confirm QT interval does not exceed 470 msec. QT interval must be calculated from a mean of all three ECG readings using Fridericia's correction (QTcF = QT/RR0.33).

During Cycle 1, ECG should be collected in triplicate prior to infusion of APR-246 and at the end of infusion (EOI) of APR-246 (6 hours after start of infusion, ± 30 min) on Days 1–4. QTcF must be calculated from a mean of all three ECG readings to confirm it does not exceed 470 msec.

If a pre-dose ECG shows  $QTcF \ge 470$  msec, the QTc reading should be confirmed by manual assessment using Fridericia's correction (QTcF = QT/RR0.33). Serum concentrations of

electrolytes should be monitored and corrected, if necessary. Additionally, concomitant medication should be reviewed and adjusted, if necessary. ECG may be repeated at any time, including the same day. APR-246 may only be administered when QTcF has returned to < 470 msec. If APR-246 is given on the same day, procedures outlined in the Schedule of Study Evaluations (Table 4) must be followed. If APR-246 cannot be administered on the same day, that dose must be omitted from the cycle.

If there is a significant change in QTcF, defined as either: a) increase > 60 msec from baseline (or pre-dose), or b) increase to an absolute value  $\geq$  501 msec, i.e. consistent with NCI-CTCAE Grade 3 QTc prolongation, QTc prolongation must be confirmed by a manual assessment of the ECG, and using Fridericia's correction (QTcF = QT/RR0.33). If confirmed, the therapy should be interrupted until a cause (electrolyte disorders or an effect of a concomitant medication) has been identified and addressed, and QTcF has returned to < 470 msec. If all other causes for clinically significant QT interval prolongation are excluded, APR-246 must be permanently discontinued.

During subsequent cycles, ECG should be collected in triplicate prior to infusion of APR-246 on Day 1 of each cycle. QTcF must be calculated from a mean of all three ECG readings to confirm it does not exceed 449 msec. If pre-dose QTcF is 450-469 msec, APR-246 may be administered, and additional triplicate ECG should be performed at the EOI (6 hours after start of infusion,  $\pm$  30 min). If post-dose ECG shows a significant change in QTcF, defined as either: a) increase > 60 msec from baseline (or pre-dose), or b) increase to an absolute value  $\geq$  501 msec, i.e. consistent with NCI-CTCAE Grade 3 QTc prolongation, QTc prolongation must be confirmed by a manual assessment of the ECG, and using Fridericia's correction (QTcF = QT/RR0.33). If confirmed, the therapy should be interrupted until a cause (electrolyte disorders or an effect of a concomitant medication) has been identified and addressed, and QTcF has returned to < 470 msec. If all other causes for clinically significant QT interval prolongation are excluded, APR-246 must be permanently discontinued. If QTcF is unchanged or there is no significant change, additional ECG is not required during that cycle.

If repeated QTcF measurements show a stable QTcF < 450 msec, or if QTcF remains stable within the interval of 450 – 469 msec with no significant change at the EOI during several cycles of treatment, reducing the number of ECGs performed in the study may be discussed with the Medical Monitor.

If a subject starts treatment with another medication known to prolong QT interval at any time during the study therapy, an additional pre- and post-dose (6 hours after start of infusion,  $\pm$  30 min) ECG should be performed on the next treatment day.

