The initial cohort of subjects will receive APR-246 at 4.5 g/day administered as an IV infusion on Days 1–4 in combination with pembrolizumab at the approved dose of 200 mg on Day 3 of each 21-day cycle. This cohort will enroll up to a maximum or 6 subjects. DLT will be assessed after 3 subjects have been enrolled in each respective cohort and the last enrolled subject has completed the 3-week safety assessment period (i.e., one cycle of combination regimen). A subject that discontinues therapy during Cycle 1 without DLT is considered evaluable for the purpose of safety only if at least 75% of scheduled doses of APR-246 were administered in the first cycle. At the first dose level of 4.5 g/day of APR-246, if  $\leq$  1 subject out of 3 experiences a DLT, 3 additional subjects will be enrolled. If  $\leq$  1 subject out of 6 experiences DLT, the dose level (4.5 g/day of APR-246) will be deemed the RP2D for that cohort. If  $\geq$  2 subjects out of the total 3 – 6 subjects in the cohort experience DLT, the study will continue enrollment at Dose Level -1 (4.0 g/day of APR-246) (see Table 1). If  $\leq$  1 subject out of 6 experiences DLT at this dose level, the dose level (4.0 g/day of APR-246) will be deemed the RP2D for that cohort. If  $\geq$  2 subjects out of 3 – 6 subjects at that Dose Level -1 experience DLT, the study will continue enrollment at Dose Level -2 (3.5 g/day of APR-246). If  $\leq$  1 subject out of 6 experiences DLT at this dose level, the dose level (3.5 g/day of APR-246) will be deemed the RP2D for that cohort. If  $\geq$  2 subjects out of 3 – 6 subjects at this dose level experience DLT, the trial will be halted and the Data Review Team (DRT) will consider potential future dosing modifications. No dose reductions in pembrolizumab are planned.

Dose Modification	APR-246 Dose
Starting Dose Level (DL)	APR-246 4.5 g/day 1.5 g (for first 45 minutes) + 3.0 g (for 5 hours 15 minutes)
Dose Level Reduction -1 (DL-1)	APR-246 4.0 g/day 1.33 g (for first 45 minutes) + 2.67 g (for 5 hours 15 minutes)
Dose Level Reduction -2 (DL-2)	APR-246 3.5 g/day 1.17 g (for first 45 minutes) + 2.33 g (for 5 hours 15 minutes)

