# 5.2 Exclusion Criteria

- 1. Known history of untreated human immunodeficiency virus (HIV)/HIV with a detectable viral load or active hepatitis B or active hepatitis C infection.
- 2. Any of the following cardiac abnormalities:
  - a. Myocardial infarction within six months prior to registration;
  - b. New York Heart Association Class III or IV (APPENDIX IV) heart failure or known left ventricular ejection fraction (LVEF) < 40%;
  - c. A history of familial long QT syndrome;
  - d. Symptomatic atrial or ventricular arrhythmias not controlled by medications;
  - e. QTcF  $\geq$  470 msec, unless due to underlying bundle branch block and/or pacemaker and with approval of the Medical Monitor.
- 3. Concomitant malignancies or previous malignancies with less than a 1-year disease-free interval at the time of signing consent. Subjects with adequately treated basal or squamous cell carcinoma of the skin, or adequately treated carcinoma in situ (e.g. cervix) may enroll irrespective of the time of diagnosis. Patients with controlled, advanced prostate cancer are permitted.
- 4. Pregnancy or lactation.
- 5. Active uncontrolled systemic infection.
- 6. An autoimmune condition requiring  $\geq$  10 mg (or equivalent corticosteroid) prednisone daily, or any other systemic immunosuppressive treatment within 28 days of first dose of study therapy.
- 7. Known history of active tuberculosis.

- 8. Current (non-infectious) pneumonitis, or a history of pneumonitis that required steroids.
- 9. A live vaccine administered within 30 days of the first dose of study treatment.
- 10. Receipt of any investigational product within 14 days or 5 half-lives prior to study treatment initiation, whichever is shortest.
- 11. Prior intolerance to pembrolizumab or other immune-oncology agents.

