# 6.3.3 Management of Nausea and Vomiting

For subjects who experience nausea and/or vomiting in association with APR-246, treatment with anti-emetics is recommended per institutional guidelines. Use of medications that prolong the cardiac QT interval is discouraged. For subjects who receive medications known to cause QT prolongation, the QT must be monitored via ECG before and after the APR-246 infusion.

• If QTc > 501 msec is observed in a subject concomitantly treated with another QT interval prolonging drug, this drug should be stopped and treatment with APR-246 may be restarted when QTc < 470 msec (refer to Section6.3.1).

A list of suggested rescue medications is provided below in Table 3.
--

Drug	Dosage	QT Prolongation a
Ondansetron	8 mg orally (PO) administered 30 minutes before	Yes
	the start of infusion or per label	
Dolasetron	100 mg PO administered within one	Yes
	hour before start of infusion or per label	
Palonosetron	0.5 mg PO administered approximately one	No
	hour prior to the start of infusion or per label	
Prochlorperazine	10 mg PO three times daily. Continue until the	No
	end of Day 4 of the cycle. When used	
	prophylactically in subsequent cycles, start the	
	day prior to Day 1 administration of APR-246	

Table 3. Medications for Managements of Nausea and Vomiting	

a Please refer to Section 6.3.1 for details on concurrent administration of medications known to cause QTc interval prolongation.

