# 9.2 Analysis Populations

*Safety population*: Subjects will be evaluable for safety if they receive at least one dose of APR-246. The safety population will be used to summarize exposure and safety parameters.

*DLT-evaluable population*: All subjects who either experience a DLT during first the 3 weeks (Cycle 1) of the study treatment or receive  $\geq$  75 % of scheduled Cycle 1 dose of APR-246 in combination with pembrolizumab and do not experience a DLT. Any individual subject who is not evaluable for DLT will be replaced by a new subject through additional subject enrollment.

*Efficacy evaluable (EE) population*: All subjects who complete at least one treatment cycle of APR-246 in combination with pembrolizumab and who have at least one post-treatment clinical response assessment. Subjects who fail to complete one treatment cycle will also be considered EE if they show clear evidence of clinically significant disease progression. The EE population will be the secondary analysis population for efficacy.

*PK population*: Subjects will be evaluable for PK if at least one post-dose sample for PK evaluation has been obtained.

*PK/Pharmacodynamic population:* All subjects who receive at least 1 dose of study drug (APR-246 pembrolizumab) and have evaluable pharmacodynamic and concentration data.

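### Exclusion 2.e can admit subjects with QTcF of 470 msec or more, but the Section 6.3.1 dosing rules have no matching exception

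*Combined protocol and SAP*

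**What the plan says.** **Eligibility.** Exclusion 2.e in Section 5.2, repeated in the synopsis, excludes QTcF of 470 msec or more "unless due to underlying bundle branch block and/or pacemaker and with approval of the Medical Monitor". A subject with a long QTcF from a conduction or pacing cause can therefore be enrolled.

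**Dosing.** Section 6.3.1 describes itself as setting the conditions for going ahead with APR-246. It contains:

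- At screening, "12-lead ECGs should be collected in triplicate to confirm QT interval does not exceed 470 msec", calculated with Fridericia's correction.
- In Cycle 1, a pre-dose QTcF of 470 msec or more leads to a manual check, electrolyte correction and a review of other medication. The ECG may be repeated, including on the same day. Then "APR-246 may only be administered when QTcF has returned to < 470 msec". If that is not achieved the same day, "that dose must be omitted from the cycle".
- After an interruption for a significant QTcF change, treatment stays on hold until a cause has been "identified and addressed, and QTcF has returned to < 470 msec".
- In later cycles, dosing is allowed at a pre-dose value of 450 to 469 msec. The later-cycle paragraph does not say what happens at a pre-dose value of 470 msec or above.

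**Secondary place.** Section 6.3.3 says "treatment with APR-246 may be restarted when QTc < 470 msec". This applies only after QTc above 501 msec in a subject also taking another QT-prolonging drug, once that drug has been stopped.

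**Evaluability.** Under Section 4.1, a subject who stops in Cycle 1 without a DLT counts "only if at least 75% of scheduled doses of APR-246 were administered in the first cycle". Section 9.2 uses the same 75% threshold and adds: "Any individual subject who is not evaluable for DLT will be replaced by a new subject through additional subject enrollment".

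**The concern.** Two current clauses of the same protocol point in opposite directions for one small group. Eligibility makes room for subjects with a fixed conduction or pacing reason for a long QTcF. The treatment rules then apply a single absolute limit to everyone, with remedies suited to a reversible cause.

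A site that follows both clauses exactly may enrol a subject who then cannot be given APR-246 in Cycle 1. A site that wants to treat that subject has to deviate from a cardiac safety rule. In the lead-in, the first course also uses up a place: the subject is exposed to trial procedures, contributes nothing to the DLT assessment, and has to be replaced.

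**Working it through.** No figure in the plan needs reproducing. The check compares the clauses and then counts doses.

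**Step 1: compare the clauses for a subject admitted under 2.e.**

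| Decision | Limit in the text | Exception for bundle branch block or pacemaker? |
|---|---|---|
| Entry (synopsis, 5.2) | excluded at QTcF ≥ 470 msec | Yes, with Medical Monitor approval |
| Screening ECG (6.3.1) | ≤ 470 msec | None |
| Cycle 1 pre-dose (6.3.1) | < 470 msec | None |
| Restart after significant change (6.3.1) | < 470 msec | None |
| Restart after QTc > 501 msec on another QT-prolonging drug (6.3.3) | < 470 msec | None |

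The only Medical Monitor discretion in the QTcF rules of 6.3.1, repeated in 8.6, concerns doing fewer ECGs when QTcF is stable below 450 msec or within 450 to 469 msec. It does not waive the dosing limit.

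**Step 2: apply the Cycle 1 rule.** Take as an assumption a subject with a stable QTcF of 480 msec from bundle branch block. The result is the same for any stable value of 470 msec or more. The manual check confirms the reading. Correcting electrolytes and reviewing medication do not remove the cause, and the repeat ECG is unchanged. The dose is omitted on Day 1, and likewise on Days 2, 3 and 4.

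**Step 3: count doses against the 75% threshold.** APR-246 is scheduled on Days 1 to 4, so there are 4 Cycle 1 doses. Share given = (4 − omitted) / 4.

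| Omitted | Share given | DLT-evaluable without a DLT? |
|---|---|---|
| 0 | 4/4 = 100% | Yes |
| 1 | 3/4 = 75% | Yes |
| 2 | 2/4 = 50% | No, replaced |
| 3 | 1/4 = 25% | No, replaced |
| 4 | 0/4 = 0% | No, replaced |

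**Step 4: could the omissions themselves count as a DLT?** Section 6.1.1 counts failure to give 75% of planned APR-246 as a DLT only when treatment-related toxicity is the reason. A conduction disorder present at entry is not that, so the subject is non-evaluable and does not count as a DLT.

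**Step 5: effect on the design.** Section 9.1 counts the lead-in maximum of 18 in DLT-evaluable patients. A replaced subject therefore does not use up any of the 18, and the rule of fewer than 2 DLTs in 6 is untouched.

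**The case against.** The best counter-argument is that the literal reading is not the only one. The Cycle 1 rule speaks of QTcF coming back below the limit, and its remedies fit an acquired, reversible rise. On that view the text simply does not address a fixed baseline that the Medical Monitor has already accepted, and the approval carries an implied permission to dose. This is a plausible account of the intent. However, the dosing sentence is unqualified, approval appears only in an eligibility criterion, and no waiver is written. If a waiver is meant, the protocol should say so.

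The second argument is that it hardly matters: each entry needs individual approval, the Medical Monitor is available to sites, and Section 8.1.2.7 refers to a detailed safety plan that may cover the case and is not among the documents. This stands as a reason for low priority. It does not make the two clauses agree.

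A reader might also infer more than the documents support:

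- *That subjects are put at cardiac risk.* The literal rule withholds APR-246, so it fails safe.
- *That such subjects can never receive study treatment.* No QTcF rule restricts pembrolizumab, and the demonstrated bar is on APR-246 in Cycle 1 while QTcF stays at or above 470 msec. The later-cycle paragraph is silent at those values, so no later-cycle pre-dose ban is shown.
- *That 6.3.3 conflicts to the same degree as 6.3.1.* It has no screening, pre-dose or later-cycle QTcF limit. It has only the restart rule with the narrow trigger described above.

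**Conclusion.** The point holds as an internal inconsistency of minor weight. Exclusion 2.e and Section 6.3.1 cannot both be followed to any purpose for a subject whose QTcF remains at or above 470 msec from bundle branch block or a pacemaker.

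Per affected subject, up to 4 of 4 Cycle 1 APR-246 doses are lost. In the lead-in, a loss of two or more without a DLT means one replacement. The full loss assumes that QTcF stays at or above 470 msec on all four days despite the manual check, corrections and repeat ECGs. The number of such subjects cannot be derived from the documents. It is probably small and may be zero.

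No sample size, RP2D rule or estimate changes. Confidence is high that the clauses disagree. It is lower on how sites would act in practice, since the Medical Monitor or the unseen safety plan might settle individual cases.

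**What to change.** Make the clauses agree by one of two routes.

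1. **Delete the exemption** for bundle branch block and pacemaker from 2.e, in both Section 5.2 and the synopsis. The downside is small: a few subjects whom the sponsor meant to allow are excluded, although 6.3.1 as written already bars them from Cycle 1 APR-246 while QTcF stays at or above 470 msec.
2. **Carry the exemption forward**, if the sponsor wants these subjects. Add it to the screening, pre-dose and restart rules of 6.3.1 and to the restart rule of 6.3.3, with an absolute hold/stop limit that is set by the sponsor's clinicians and written into the protocol.

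Under the second route the absolute limit has to be stated, because the existing change-from-baseline trigger alone would be loose. From a baseline of 470 msec, a rise of more than 60 msec is first met at 470 + 61 = 531 msec. The existing absolute trigger of 501 msec is met after a rise of 501 − 470 = 31 msec.

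The choice between the routes is clinical. Either is a short wording change, but it alters eligibility or treatment rules. It is therefore a protocol amendment that needs IRB/IEC approval under Sections 10.3 and 11.2, and could be bundled with the next amendment.

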# 6.3.2 Management of CNS Adverse Events

If, during the administration period of APR-246, a subject experiences an AE that could be considered to originate from the CNS (e.g. dizziness, vertigo, nausea), medical management

is recommended as per institutional standard of care. Prompt discussion with the Medical Monitor is recommended.

Treatment with prochlorperazine 10 mg orally three times daily (tid) PRN has been reported to effectively treat CNS AE. Prochlorperazine may also be used prophylactically. When prochlorperazine is used prophylactically, it is recommended that treatment start the day prior to the Day 1 and continue at 10 mg tid through Day 4 as needed. It is important to record the dose and time of prochlorperazine administration in the eCRF.

In addition, dose modifications have been successfully used to manage CNS AEs occurring during the infusion (Table 2). For any clinical AE Grade  $\geq$  3, the infusion should be interrupted and if the AE resolves to CTCAE  $\leq$  Grade 1 within 2 hours, the infusion may be resumed at the same infusion rate. If similar symptoms recur during re-challenge the infusion should be interrupted.

If an AE lasts longer than 2 hours, then the APR-246 infusion should be discontinued for that day, the remaining drug should be discarded.

Worst toxicity	Dose Modifications for APR-246
Grade 1	Maintain dose level
Grade 2	If resolved to $\leq$ Grade 1 with medical therapy, continue same dose level. If not resolved despite treatment interruption and maximal medical therapy, stop infusion and $\downarrow$ 1 dose level for subsequent dose
Grade ≥ 3	Stop infusion and give medical therapy. If resolved (to $\leq$ Grade 1) with medical therapy, infusion may continue at the investigator's discretion. $\checkmark$ 1 dose level for subsequent dose
Grade 4	Permanently discontinue subject from APR-246.

Table 2. Management of CNS Adverse Events (Dizziness, Dyskinesia and Ataxia)

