# 8.1.2 Reporting of Adverse Events

#### 8.1.2.1 Adverse Events

An AE is any untoward medical occurrence in a subject or clinical investigation subject administered a pharmaceutical product that does not necessarily have a causal relationship with the treatment. An AE can be any unfavorable and unintended sign (including a laboratory finding), symptom or disease temporally associated with the use of a medicinal (investigational) product, whether or not related to the medicinal (investigational) product.

The AE reporting period starts at study treatment initiation. At each evaluation, subjects should be interviewed in a non-directed manner to elicit potential adverse reactions from the subject. The occurrence of an AE will be based on changes in the subject's physical examination, laboratory results, and/or signs and symptoms.

All AEs (except Grade 1 and 2 laboratory abnormalities that do not require an intervention), regardless of causal relationship, are to be recorded in the eCRF and source documentation. The investigator must determine the intensity of any AEs according to the NCI-CTCAE version

5.0 and their causal relationship. Those AEs not covered by these criteria will be graded as follows:

- 1. Mild: Discomfort noticed, but no disruption of normal daily activity. Prescription drug not ordinarily needed for relief of symptom but may be given because of personality of subject.
- 2. Moderate: Discomfort sufficient to reduce or affect normal daily activity. Subject is able to continue in study; treatment for symptom may be needed.
- 3. Severe: Incapacitating, severe discomfort with inability to work or to perform normal daily activity. Severity may cause cessation of treatment with test drug; treatment for symptom may be given and/or subject hospitalized.
- 4. Life-Threatening: Symptom(s) place the subject at immediate risk of death from the reaction as it occurred; it does not include a reaction that, had it occurred in a more serious from, might have caused death.
- 5. Fatal: Event caused the death of the subject.

AEs will be followed until resolution or stabilization while the subject remains on-study. Once the subject is removed from study, events thought to be related to the study medication will be followed until resolution or stabilization, unless, in the investigator's opinion the event is unlikely to resolve due to the subject's underlying disease, or until the subject starts a new treatment regimen or the subject is lost to follow-up.

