# 8.1.2.4 Serious Adverse Event (SAE)

An SAE is defined as any untoward medical occurrence that at any dose:

- 1. Results in death,
- 2. Is life-threatening (i.e., the subject was at risk of death at the time of the event. It does not refer to an event which hypothetically might have caused death if it was more severe),
- 3. Requires inpatient hospitalization or prolongation of existing hospitalization excluding that for pain management, disease staging/re-staging procedures, or catheter placement unless associated with other serious events,
- 4. Results in persistent or significant disability/incapacity, or
- 5. Is a congenital anomaly/birth defect.

Important medical events that may not result in death, be life-threatening, or require hospitalization may be considered serious adverse drug events when, based on appropriate medical judgment, they may jeopardize the subject and may require medical or surgical intervention to prevent one of the outcomes listed above.

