# 8.1.2.6 Reporting of Serious Adverse Events

AEs classified as serious require expeditious handling and reporting to Sponsor's monitoring CRO to comply with regulatory requirements.

For any SAE that occurs while a subject is on-study; within 30 days of the last study treatment administration, regardless of any opinion as to the relationship of the SAE to the study treatment; or if any SAE that the investigator feels is related to the study treatment occurs later than 30 days after the last study treatment administration, the Sponsor's monitoring CRO must be notified immediately (within 24 hours of becoming aware of the event) by email, fax or telephone. Notification by email is preferred. The email address, fax and telephone numbers listed below may be used during both business and non-business hours. During non-business hours a recorded message will provide the telephone caller with the contact information for the on-call monitor.

All SAEs require that a Serious Adverse Event Report Form be completed and forwarded either via facsimile or as a PDF via email to Sponsor's monitoring CRO at the fax number or email listed below within 24 hours of becoming aware of the event.

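### Section 6.3.2: two permissions to restart APR-246 are written for Grade 3 and above, so they overlap the Table 2 row that requires permanent discontinuation at Grade 4

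*Combined protocol and SAP*

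**What the plan says.** Section 6.3.2 of the protocol deals with CNS adverse events during APR-246 dosing through a short body text and Table 2.

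- **Body text.** For any clinical AE of Grade 3 or higher the infusion is interrupted. If the event comes down to Grade 1 or less "within 2 hours, the infusion may be resumed at the same infusion rate". The following paragraph sets a limit: "If an AE lasts longer than 2 hours, then the APR-246 infusion should be discontinued for that day".
- **Table 2, event types.** The table's title, "Management of CNS Adverse Events (Dizziness, Dyskinesia and Ataxia", names three event types. The body text points to the table for CNS events that occur during the infusion.
- **Table 2, row for Grade 3 and above.** The infusion is stopped and medical therapy given. If the event resolves to Grade 1 or less "with medical therapy, infusion may continue at the investigator's discretion", and the subsequent dose drops by one dose level.
- **Table 2, row for Grade 4.** "Permanently discontinue subject from APR-246". The row makes no exception for events that resolve.

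Neither the body text nor the table says which instruction governs when more than one applies.

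**The concern.** Grade 4 lies inside a category written as Grade 3 and above. A Grade 4 event of one of the three named types that resolves during the infusion visit is therefore covered by two texts that allow APR-246 to go on and by one that ends it for good. A reader has to infer the order of precedence.

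What is at stake is how a stopping rule is applied at the infusion chair. The body text is a complete instruction in itself: interrupt, wait up to 2 hours, resume at the same rate. Someone working from that paragraph alone would find nothing there that excludes Grade 4. The study is multicenter and allows outpatient dosing, so sites need one explicit rule for the most severe non-fatal grade.

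**Working it through.** No sample size, error rate or other computed figure is involved. The check applies each rule in section 6.3.2 to the same event and then looks for a precedence statement.

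**Step 1. Fix the event.** Dizziness, dyskinesia or ataxia during the APR-246 infusion, with Grade 4 as the worst grade.

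**Step 2. Apply the rules.**

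- *Resolved to Grade 1 or less within 2 hours.* The body text permits resumption at the same rate. The Table 2 row for Grade 3 and above permits continuation and calls for a lower dose level next time. The Grade 4 row requires permanent discontinuation. The count is two optional permissions and one mandatory stop.
- *Resolved to Grade 1 or less only after 2 hours.* The body-text permission no longer applies and that day's infusion ends. The row for Grade 3 and above carries no time limit of its own and still looks ahead to a reduced subsequent dose, while the Grade 4 row allows no further dose. The overlap remains for later days.
- *Same event types with worst grade 3.* Only the body text and the row for Grade 3 and above apply. The Grade 4 row is not engaged, so the permanent stop raises no conflict here.

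The problem is confined to Grade 4 and comes from the lower-bound wording, which appears both in the body text and in the table.

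**Step 3. Look for precedence.** Sections 5.4.1, 6.1, 6.1.1, 6.2 and 6.3 contain no sentence that ranks the Grade 4 row above the two permissions. Section 6.2 has a general discretionary restart rule, but it sets no priority in relation to Table 2.

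**Step 4. Check for an effect on the trial's results.** Under section 6.1.1, a Grade 4 non-hematologic toxicity in Cycle 1 that is at least possibly related to APR-246 is a DLT in its own right. Whether the infusion is then resumed or stopped does not change that classification, so the DLT count behind the RP2D is the same under either reading. No analysis in section 9 turns on the choice.

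**The case against.** The strongest reply is that there is no real conflict. Both permissions are optional, and the Grade 4 instruction is unconditional. A site that discontinues breaches nothing; a site that resumes breaches the Grade 4 row. The step down in dose has nothing to act on once the drug is permanently stopped. Table 2 selects its row by worst toxicity, so a worst-grade-4 event has a row of its own, and that row would have no effect if it did not govern. The body text comes straight after a pointer to Table 2 and can be read as introducing it. Section 5.4.1 adds a mandatory stop when the investigator judges that an adverse experience makes continued participation an unacceptable risk, and the person with discretion to resume is bound by that rule.

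Most of this stands. It shows what the authors meant and makes resumption after a Grade 4 event unlikely. It does not supply the missing sentence: the precedence is inferred, and the 5.4.1 stop depends on case-by-case judgment.

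A reader might infer something stronger, namely that the protocol authorises re-exposing patients on the same day after a life-threatening event. The documents do not support that, for three reasons.

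- The Grade 4 row forbids it for the three event types.
- The protocol's description of its fourth severity level, "Life-Threatening: Symptom(s) place the subject at immediate risk of death from the reaction as it occurred", belongs to a scale for AEs that CTCAE does not cover. Nothing shows that dizziness, dyskinesia or ataxia falls outside CTCAE, and whether CTCAE defines a Grade 4 for each of them is not given in the documents.
- No rate is given for such events, or for their resolution within 2 hours.

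It is also tempting to rest the case on SAE reporting. An event that "Is life-threatening (i.e., the subject was at risk of death at the time of the event" is serious under section 8.1.2.4, and the sponsor's monitoring CRO "must be notified immediately (within 24 hours of becoming aware of the event". That duty is a reporting step. It is not what stops or restarts an infusion, so it neither resolves the overlap nor makes it worse. Discussion with the Medical Monitor under 6.3.2 is recommended, not required.

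**Conclusion.** The text is wrong as written, and the consequence is small. In section 6.3.2 the body-text permission to resume and the Table 2 row for Grade 3 and above both literally include Grade 4, which contradicts the Grade 4 row for dizziness, dyskinesia or ataxia during infusion that resolves to Grade 1 or less. The intended rule can be found by a careful reader but is not stated.

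This is a minor internal inconsistency in a safety stopping rule. It has no effect on DLT counts or analyses, and its frequency cannot be derived from the documents. The conclusion rests on the wording of 6.3.2 and on the absence of a precedence statement in the sections searched. It assumes nothing about how often Grade 4 events occur or how CTCAE grades these terms. It is worth correcting because the row exists to stop treatment and should not depend on inference.

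**What to change.** Three edits within section 6.3.2:

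1. In Table 2, relabel the row for Grade 3 and above as Grade 3.
2. In the body text, keep interruption of the infusion for Grade 3 and above, but allow resumption only for Grade 3.
3. Add one sentence: *For Grade 4 events covered by Table 2, do not resume the infusion; permanently discontinue APR-246.*

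The cost is a few words. Design, sample size, DLT rules and analyses stay as they are.
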